### **I. Recruitment and Enrollment**

Our primary patient resource is from OU Physician Neurology Clinic and Allied Health Clinical Network. We will also seek referrals from clinicians in the Oklahoma City areas and recruit stroke survivors residing in these two areas who wish to participate in the study. The recruitment method will include doctor referrals and direct contact (if study doctor's patients) via the study doctor.

Stroke participants will be examined by the study doctor to verify their admissibility to the study based on the inclusion criteria. Participants will then undergo the upper extremity portion of the Fugl-Meyer Motor Assessment, and a structured interview pertaining to the inclusion criteria stated above.

Our clinician investigators and/or clinical research assistant will discuss the proposed study with potential participants and answer all questions. Potential participants will also be introduced to laboratory facilities at study sites. The PI will review the Institutional Review Board-approved consent form and HIPAA authorization with the participant and give them a copy of the signed consent form prior to any experimental procedures. Upon the request, we will allow the participant to have additional time to consider the consent and discuss it with their family member or physician. The participant must sign both the consent form, as well as the HIPAA form prior to participating in this study.

### **J. Risks and Benefits**

The self-adhesive surface electrodes used to record muscle activity (EMG) may produce minor irritation of the skin; there is also the possibility of an allergic reaction to the electrode paste. The possibility of irritation will be minimized by cleaning the skin with alcohol before and after the application of the electrodes. There is a similar possibility of scalp irritation due to a reaction to the use of EEG/tDCS electrodes.

The tDCS may cause transient itching and tingling at the beginning of the delivery of stimulation due to the change of voltage/current as it ramps up to the targeted intensity. However, most people reported that these are very mild and fade quickly. A small number of participants may report moderate fatigue, particularly during, but not after stimulation. Minor scalp skin irritation may occur but will be minimized by screening participants who self-report having sensitive skin (based on the tDCS Safety Screening Tool (TSST)(16)).

If stroke patients participate in this study, possible benefits may include an improved ability to control their paretic arm during movement tasks. Benefits may or may not continue after the research has ended. Possible benefits to others include an enhanced understanding and treatment of movement disturbances following a stroke.

## **L. Statistical Analysis Plan**

The statistical and power analysis will be led by [name], Assistant Professor of Research in Department of Biostatistics & Epidemiology, Hudson College of Public Health within the University of Oklahoma Health Sciences Center. The obtained preliminary data will refine our power analysis to provide a more precise estimation of sample size for a future full trial. The effect of HD-tDCS is determined by the change in Fugl-Meyer upper extremity Part A score (primary outcome measure), change in Transcranial Magnetic Stimulation (TMS)-Evoke Motor-evoked Potentials (MEP, secondary outcome measures), and change in Brain Symmetry Index (other outcome measures). All statistical analysis was completed using commercial software Statistical Analysis Systems (9.4, SAS, Carey, NC, USA). After checking for and finding no evidence of a non-normal outcome measure distribution, we analyzed the data using generalized estimating equation (GEE) in SAS using PROC GENMOD. The fixed factors are group (anodal, cathodal, sham), time (pre and post intervention), and their interaction, and the random factor is subject ID. This technique uses correlated linear models for each outcome variable (17,18).

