**Aim 1. Demonstrate the feasibility of stroke subject recruitment and retainment.** Our pilot power analysis determined that at least 40 stroke patients will be needed in a full R01 trial. We **hypothesize** that our experimental site at the OUHSC campus has the full ability to recruit 12 eligible patients in one year and retain most of them to complete this trial (detailed in Aim 2).

**Aim 2. Determine the effect of the targeted HD-tDCS on reducing the upper limb motor impairment.** We hypothesize that: 1) facilitating the ipsilesional primary motor cortex will improve the function of the damaged corticospinal tract and therefore, reduce upper limb muscle synergies. 2) inhibiting the contralateral premotor cortex will reduce the maladaptive use of the cortico-reticulospinal tract and thus, also reduce impairment. This randomized, double-blinded, sham-controlled cross-over study will include the anodal HD-tDCS targeting the **ipsilesional primary motor cortex (Aim 2a)**, and the cathodal HD-tDCS over the **contralateral premotor cortex (Aim 2b)**, compared to sham stimulation. We will use a subset of Fugl-Meyer Upper Extremity assessment which is mainly related to the muscle synergies as the primary outcome measure. The TMS-induced motor-evoked potentials (MEP) will be measured to determine the use of ipsilesional corticospinal tract and the contralateral cortico-reticulospinal tract, with the MEP latency as the secondary outcome measure. Resting-state EEG will also be obtained to have the *brain symmetry index* as the third outcome measure for evaluating the acute effect of HD-tDCS on brain plasticity.

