### B. Background and Significance

Stroke survivors account for 795,000 adults per year and approximately 7 million individuals living in the US (data from CDC and AHA websites). In stroke rehabilitation research, individuals exhibiting moderate-to-severe upper limb impairment after stroke are underserved and under-investigated. Reviews of existing studies indicate that treatments are minimally in improving of upper limb function(12). Moreover, constraint-induced therapy, a well-established clinical technique, requires a large dosage (30-40 hours/week) that is not always feasible in the current healthcare climate nor can it be used in individuals with more severe motor impairment(12). New interventions are needed that can easily translate to the clinic. Improved intervention strongly relies on our understanding of neural circuitry changes in the motor system after a stroke and how they could be positively and specifically influenced by neuro-rehabilitation technology. Previous studies (including the PI's R21 study(3-5)) found that post-stroke muscle synergy impairment is associated with increased recruitment of the contralateral cortico-reticulospinal tract, following damage to the corticospinal tract at the lesioned side(2, 6) (Fig.1). This finding provides potential neuro-targets to reduce muscle synergies, i.e., facilitating the use of the lesioned corticospinal tract or inhibiting the recruitment of the contralateral cortico-reticulospinal tract. This pilot study will provide the first preliminary data to evaluate the effect of our novel targeted HD-tDCS intervention on reducing upper limb muscle synergies. **This proposal is significant because it targets patients who have had strokes and continue to experience muscle synergy impairment with limited options for improving upper limb movement.**

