### C. Preliminary Studies/Progress Report

The contact PI [name] has collected pilot data from both his previous institute Northwestern Medicine, as well as in his current Tulsa lab (OU #IRB 12550). The data demonstrated the feasibility of proposed HD-tDCS technology, showing both anodal (over the ipsilesional primary motor cortex) and cathodal (over the contralateral premotor cortex) HD-tDCS reduced the expression of muscle synergies (Fig. 2). The anodal HD-tDCS reduced the latency of MEP of the damaged corticospinal tract while the cathodal HD-tDCS increase the latency of the MEP of the contralateral cortico-reticulospinal tract. Thus, the previous pilot data support our hypotheses that 1) facilitating the ipsilesional primary motor cortex will improve the function of the damaged corticospinal tract and enhance upper limb movement. 2) inhibiting the contralateral premotor cortex will reduce the maladaptive use of the cortico-reticulospinal tract and reduces the synergy impairment.

[figure not shown]

Fig. 1. Reduced expression of muscle synergies after the targeted HD-tDCS. A1-3 Anodal, C1-2 Cathodal.

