### D. Research Design and Methods (What, When, How, Where)

The statistical analysis of our preliminary data indicated that 40 stroke participants are required to ensure the detection of the significance of our results in a complete trial. We will screen up to 50 patients to ensure we can enroll at least **12 stroke** participants in the first year as the pilot sponsored by OSCTR pilot grant. The participants living around the Oklahoma City area (main site) will be asked to come to:

- OU Physician Neurology Clinic [name] (the primary site).
- College of Allied Health at the University of Oklahoma Health Sciences Center located at [name] (the secondary site)

Baseline standard clinical screens including the Fugl-Meyer Motor Assessment (Upper Extremity Portion) will be conducted prior to any intervention trials.

**Overall Overview of Trial Design.** This **sham-controlled cross-over study design** will include three visits: 1) anodal stimulation targeting ipsilesional hemisphere, 2) cathodal stimulation at the contralesional hemisphere, 3) sham stimulation. The sequence of the stimulations will be **randomized and double-blinded**. After each intervention, there will be a 2-week **wash-out period** (minimum) prior to providing the next intervention in the sequence. Each visit will last up to 3 hours including the preparation time and breaks.

We will use neuro-navigation high-definition tDCS (NNG HD-tDCS) to target specific brain regions in a novel and precise manner. A subject-specific head model will be built to evaluate the effect of lesion size and location on the electrical field of tDCS. The MR images (or CT images) will be used to build these subject-specific head models. The stimulation electrode montage and inter-electrode distance will be carefully examined by computer simulation to determine the optimal setup and dosage for NNG HD-tDCS. Based on our pilot test, the stimulation dosage will be set as 2 mA, 20 min, the dosage for best-influencing neuroplasticity according to the safety guidelines of HD-tDCS(13,14).

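### Will the full trial's sample size be refined on the active-minus-sham difference, or on an uncontrolled pre-post change?

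*Combined protocol and SAP*

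**What the plan says.** Two places give the full-trial number. Aim 1 in Section A: "Our pilot power analysis determined that at least 40 stroke patients will be needed in a full R01 trial". Section D: "The statistical analysis of our preliminary data indicated that 40 stroke participants are required to ensure the detection of the significance of our results". Neither gives an endpoint, contrast, significance level, power, effect size, SD or number of cases.

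Section B describes the present study this way: "This pilot study will provide the first preliminary data to evaluate the effect of our novel targeted HD-tDCS intervention". Section C reports earlier data from the investigator's previous institute and current laboratory, and says that both anodal and cathodal "HD-tDCS reduced the expression of muscle synergies (Fig. 2). The anodal HD-tDCS reduced the latency of MEP of the damaged corticospinal tract". The figure caption reads: "Reduced expression of muscle synergies after the targeted HD-tDCS. A1-3 Anodal, C1-2 Cathodal". Section C mentions neither sham nor Fugl-Meyer Part A.

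Aim 2 in Section A defines the comparison for the pilot. Each active stimulation is "compared to sham stimulation. We will use a subset of Fugl-Meyer Upper Extremity assessment which is mainly related to the muscle synergies", and that subset is the primary outcome.

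Section L then says "The obtained preliminary data will refine our power analysis to provide a more precise estimation of sample size for a future full trial", and next: "The effect of HD-tDCS is determined by the change in Fugl-Meyer upper extremity Part A score (primary outcome measure". Its model has group (anodal, cathodal, sham), time (pre, post) and their interaction as fixed factors.

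**The concern.** Read in sequence, these statements raise two doubts.

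The first is the origin of the 40. Section D takes it from preliminary data, Section B calls the present pilot the first preliminary data on the effect, and Section C describes earlier data with no sham condition. A reader may infer that the 40 was sized on the change after active stimulation alone.

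The second is the update. Section L speaks of refining the number and, in the next sentence but one, defines the effect as a change in score without adding that it is relative to sham. A one-arm pre-post change includes anything that sham would also produce, such as retest or expectation effects on a scale repeated at the same visit. It also leaves out the variance added by comparing two visits. If the 40 had that basis and the refined number kept it, the full trial would be sized on a quantity that it does not test.

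**Working it through.** **1. Can the 40 be reproduced?** No, because no inputs are stated. It can only be solved backwards. Assume a paired t-test, two-sided 5% and 80% power. The standardised effect d for which 40 participants give 80% power (noncentral t) is 0.454. The normal approximation gives (1.960 + 0.842)/√40 = 0.443. No such effect appears in the documents, so it cannot be confirmed or refuted.

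**2. How much could the basis matter, if the suspicion were true?** Suppose that 40 is right for a one-arm pre-post change, that the SD of change is equal under active and sham, and that the full trial is a crossover. Let p be the sham change as a fraction of the active change, and ρ the within-person correlation of change scores between visits. The standardised active-minus-sham effect is then

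e = d(1 − p) / √(2(1 − ρ)), with d = 0.454.

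For example, p = 0.25 and ρ = 0.5 give e = 0.454 × 0.75 / 1 = 0.341.

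| Sham change / active change | N for 80% power at ρ = 0.3 / 0.5 / 0.7 | Power with 40 at ρ = 0.3 / 0.5 / 0.7 |
|---|---|---|
| 0 | 56 / 40 / 25 | 66% / 80% / 95% |
| 0.10 | 68 / 49 / 31 | 57% / 71% / 90% |
| 0.25 | 97 / 70 / 43 | 43% / 56% / 77% |

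Forty is enough when ρ is at least 1 − (1 − p)²/2, that is 0.50, 0.595 and 0.72 for the three rows. The answer can fall on either side of 40. Every input except the 40 is assumed. If the 40 already came from a sham contrast, the table does not apply.

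**3. Does the plan, followed as written, yield the right contrast?** Write the mean score as group + time + group × time, with sham and pre as reference levels. The interaction coefficient for anodal at post is

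(anodal post − anodal pre) − (sham post − sham pre),

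and the cathodal coefficient has the same form. Each is the active-minus-sham difference in change. The first outcome put through this model is Fugl-Meyer Part A, and the design collects pre and post scores under sham from the same people. The mean difference comes from the model, and its within-person SD comes from the same data. No passage suggests that the sham visit would be set aside for the update.

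**4. Do Sections B, C and D contradict each other?** Not necessarily. Section C presents the earlier data as showing feasibility. Section B can mean that this pilot gives the first controlled data on the effect. Section D can then refer to the earlier, smaller data set. The wordings of Aim 1 and Section D can describe one and the same calculation. The documents do not say that the cases in the Section C caption produced the 40.

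**5. How precise could any refinement be?** With 12 people and 11 degrees of freedom, the 95% interval for an SD runs from √(11/χ²₀.₉₇₅) = 0.71 to √(11/χ²₀.₀₂₅) = 1.70 times the estimate. At a fixed target difference, a calculated 40 would then span 22 to 112. This imprecision belongs to a pilot of this size and is present whichever contrast is named.

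**The case for a change.** The strongest case for acting is that the gap is real and cheap to close. The 40 is stated twice without inputs, the only earlier data described have no sham, and the sentence promising a refined number is followed by a definition of effect as change. Reading Section B as first controlled data does not dispose of the point, because the 40 would then rest on uncontrolled data. Sizing the full trial is also a use of the pilot that Section L itself names. Fixing the contrast before results are seen would prevent a later choice of the more favourable quantity.

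Part of this stands: the inputs behind the 40 are not given, and no sentence links the interaction term to the sample-size update. The inference drawn from it does not stand. That the Section C cases produced the 40 is a guess from a short summary and a caption whose figure is not shown. That the update would ignore sham runs against Aim 2 and against the only model in Section L. The table above measures a hypothetical and does not show a defect in this plan.

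**Conclusion.** The concern does not call for a change. Aim 2 and the group-by-time model together already define the quantity that a sample-size update should use, and a statistician carrying out the plan would take it from there. The residue is missing detail: unstated inputs for a provisional number and one unstated link. It concerns a future trial, which would need its own justification for its size.

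Nothing in the pilot moves. The 12 rests on one-year recruitment, and the analysis and effect estimates do not depend on the 40. The illustrative range of 25 to 97 depends on an assumed one-arm origin for the 40, two-sided 5%, 80% power, equal SDs, a crossover full trial, and chosen values of ρ and the sham fraction. It extends in both directions and does not show that 40 is too small. The conclusion assumes that the update will use the Section L model for the primary outcome. It would be different if the documents said that the sample size would be recalculated from change in the active arms alone, and they do not say so.

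### The SAP plans GEE on about 12 participants with no small-sample method; with robust Wald inference each active-versus-sham test at a nominal 5% level runs at about 8.7%, and its 95% interval is about 15% too narrow

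*Combined protocol and SAP*

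**What the plan says.** Section L of the combined protocol and SAP holds the whole analysis plan. It says that "we analyzed the data using generalized estimating equation (GEE) in SAS using PROC GENMOD". On the model it says: "The fixed factors are group (anodal, cathodal, sham), time (pre and post intervention), and their interaction, and the random factor is subject ID". The next sentence adds: "This technique uses correlated linear models for each outcome variable". It names no alpha level, type of standard error, working correlation, type of test, reference distribution, degrees of freedom or small-sample correction, and no other section supplies them.

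On size, section D says "We will screen up to 50 patients to ensure we can enroll at least" 12 participants. Aim 1 in section A expects to "recruit 12 eligible patients in one year and retain most of them to complete this trial". Section L also says how the results will be used: "The obtained preliminary data will refine our power analysis to provide a more precise estimation of sample size for a future full trial".

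**The concern.** GEE inference with robust standard errors relies on a large number of clusters. Here the cluster is the participant, and there are about 12. Two things then go wrong in the same direction: the robust variance is biased downward, and the normal reference distribution has tails that are too light. The group-by-time contrasts affected are the ones that answer Aims 2a (anodal versus sham) and 2b (cathodal versus sham). A stimulation with no effect would be called effective or harmful more often than the reader of a 5% test expects, and the reported intervals would overstate precision.

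The description also mixes two kinds of model. A GEE has a cluster and a working correlation but no random factor, so "and the random factor is subject ID" belongs to a mixed model, while the sentence on correlated linear models fits participant as the cluster. An analyst could follow either reading, and their error rates differ.

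**Working it through.** **The plan's own figure.** The only sample-size figure from a power analysis is 40, for the later full trial. It comes without alpha, power, effect size or SD, so it cannot be reproduced. Nothing below depends on it.

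**Inputs from the documents.** n = 12 participants (section A, Aim 1; section D, at least 12); three conditions with a pre and a post measurement each (sections D and L); the model terms in section L; an outcome treated as normal (section L).

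**Assumptions.** Two-sided 5% level; robust standard errors without correction; Wald tests; complete data unless stated. No SD, within-person correlation or effect size is needed for the error rates or the width ratios.

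**One active-versus-sham contrast (1 df).** For participant i, let dᵢ = (post − pre, active) − (post − pre, sham), and let s be the usual SD of the dᵢ with divisor n−1.

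- The GEE estimate of the contrast is the mean of the dᵢ.
- Its robust SE is √Σ(dᵢ − d̄)² / n = (s/√n)·√((n−1)/n). GEE fits gave this same SE under independence and exchangeable working correlation.
- Hence robust z = t·√(n/(n−1)), where t follows t(n−1) under no effect.
- At n=12 the cutoff of 1.96 acts on t(11) as 1.96·√(11/12) = 1.877. The correct cutoff is 2.201.
- True size = P(|t₁₁| > 1.877) = 0.0873. Coverage = 1 − 0.0873 = 91.3%.
- Width ratio = 1.877/2.201 = 0.853, so the interval is 15% too narrow.

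**Interaction (2 df).** The uncorrected Wald statistic is W = [2n/(n−2)]·F(2, n−2). At n=12 the size is P(F(2,10) > 5.991·10/24 = 2.496) = 0.132.

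| n | Wald size, 1 df | Interval too narrow by | Wald size, 2 df |
|---|---|---|---|
| 10 | 9.6% | 18% | 15.3% |
| 11 | 9.1% | 16% | 14.1% |
| 12 | 8.7% | 15% | 13.2% |
| 16 | 7.7% | 11% | 10.8% |
| 20 | 7.1% | 9% | 9.5% |

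**Partial repairs at n=12.**

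- n/(n−1) variance with 1.96: P(|t₁₁| > 1.96) = 7.6%.
- t(11) with the uncorrected variance: P(|t₁₁| > 2.201·√(11/12)) = 5.9%.
- Corrected W/2 referred directly to F(2,10): P(F > 4.103·10/11) = 6.2%.

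**Full repair.** With the n/(n−1) variance and t(11), the contrast is the one-sample t test on the dᵢ. Its size is exactly 5% for normal differences with complete data. For the interaction, with W from the corrected variance, W·(n−2)/(2(n−1)) follows F(2, n−2) exactly under the same conditions.

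**Simulation.** GEE with exchangeable working correlation, 12 participants × 6 observations, 60,000 runs. Missing visits are an assumption.

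| Participants missing one visit | Wald, 1 df | Wald, 2 df | Proposed t(11) | Proposed scaled F |
|---|---|---|---|---|
| 0 | 0.088 | 0.134 | 0.050 | 0.051 |
| 2 | 0.090 | 0.136 | 0.052 | 0.053 |
| 3 | 0.090 | 0.138 | 0.052 | 0.054 |

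With change scores in whole points (assumed SD 1 to 3 points, 400,000 runs), the Wald test ran at 0.085 to 0.089 and the proposed t(11) test at 0.049 to 0.050. With the anodal change SD doubled, the proposed tests stayed at 0.050.

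**The case against.** The strongest objection is that 8.7% describes one branch of a choice the SAP does not make. It needs a 5% level, robust standard errors and a Wald test. A robust score statistic, nW/(n+W), gives 4.4% for one contrast and 3.15% for the interaction at n=12. Model-based exchangeable standard errors ran at 0.6% or less in simulation, with the between-subject SD assumed to be five times the residual SD. The random-factor wording also allows a mixed-model reading, and a mixed model with small-sample degrees of freedom could avoid the problem. All of this stands as a limit on the figure. It does not answer the concern: the plan leaves the error rate of its main tests anywhere in that range, with the choice open after the data are seen. A score test also leaves the intervals uncorrected.

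A second objection is that this is a pilot. Point estimates are unaffected with complete data, no go/no-go rule depends on the intervals, and the later power analysis needs an SD rather than a p-value. That limits the harm to over-optimistic p-values and intervals for Aims 2a and 2b. Any effect on the planned 40 cannot be quantified from the documents.

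A third is that the repair is exact only for the model as written. With period terms added (12 participants, all six sequences twice, independence working model, 100,000 runs), the corrected test ran at about 6.1% and the uncorrected Wald test at about 10%. The SAP has no period term, and the correction still removes most of the excess, but it would then be approximate.

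**Conclusion.** The concern holds and should be fixed. The omission is certain. Its size is exact for complete data, normal differences, robust Wald inference and a two-sided 5% level: at n=12, a false-positive rate of about 1 in 11 instead of 1 in 20 for each active-versus-sham contrast, with the interval and interaction errors shown above. With 10 completers the error rate is 9.6%. If model-based standard errors or a subject-only random intercept were used instead, the tests could be conservative, by an amount that depends on variances the documents do not give.

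**What to change.** Keep GEE with group, time and their interaction, and amend section L as follows.

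- Describe participant as the cluster and drop the reference to a random factor.
- State the alpha level, and that robust standard errors are used with the variance multiplied by n/(n−1), n being the number of participants.
- Use t(n−1) for the anodal–sham and cathodal–sham contrasts and their 95% intervals. With complete data these are paired t tests on the change scores, which gives a simple check on the output.
- For the interaction, compute W from the corrected variance and refer W·(n−2)/(2(n−1)) to F(2, n−2), not W/2.
- For the full-trial power analysis, take the SD directly from the within-person differences in change, active minus sham.

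The cost is SAP wording and a short calculation on the robust covariance matrix. Compared with the uncorrected robust output, intervals are 1/0.853 = 1.17 times as wide at n=12 and 1.22 times at n=10. Apparent power falls. For an effect of 0.9 SD of the within-person difference (an illustrative value; noncentral t with noncentrality 0.9√n), it goes from 88% to 81% at n=12 and from 83% to 72% at n=10. Part of the higher figure came from the inflated error rate. With missing visits, or if a period term is added, the correction is approximate, and the SAP should say so.

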**Assessments and Outcome Measures.** The following assessments will be performed for baseline, pre- and (immediate) post-intervention time frames. The Fugl-Meyer-Upper Extremity (FM-UE) assessment Part A - mainly related to the muscle synergies and serves as the primary outcome measure. This subset FM-UE assessment increases the sensitivity of the measure and reduces the test time from 30 mins (full assessment) to 10 mins. The TMS-evoke motor-evoked potentials (MEP) will be measured to determine the use of the ipsilesional corticospinal and the contralesional cortico-reticulospinal tract, with MEP latency serving as the secondary outcome measure. The single or paired-pulse TMS will be applied at the respective hotspots for the elbow flexor muscle, i.e., Biceps Brachii, over the ipsilesional primary motor cortex (from which the corticospinal tract originates) and contralesional premotor cortex (from which the cortico-reticulospinal tract originates) with reference to the impaired arm. A 3 min 20 channel Resting-state EEG will also compute the *brain symmetry index* (BSI) as the third outcome measure for evaluating the acute effect of HD-tDCS on brain plasticity. The BSI is defined as the mean of the absolute value of the difference in the mean hemispheric amplitude spectrum; values range from 0 (no asymmetry, normal control) to 1 (maximal asymmetry, more impaired brain function). The total three assessments will last for ~33 min (10 mins subset FU-UE assessment, ~10 mins TMS MEP, and 3 mins EEG recording plus 10 mins procedure time), which will be within the effective period of HD-tDCS. Baseline measurement will be performed at the beginning of the study on the first visit. To ensure there is no carry-over effect, we will compare the outcomes of pre-stimulation measurement with the baseline for each visit.

All recorded data will be de-identified for the analysis. Identifiers might be removed, and the de-identified information may be used for future research without additional informed consent from the subject.

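### The three-visit cross-over model has no visit or visit-by-time term, and the plan does not say that the stimulation orders are balanced

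*Combined protocol and SAP*

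**What the plan says.** Section L (Statistical Analysis Plan) gives the whole model: "The fixed factors are group (anodal, cathodal, sham), time (pre and post intervention), and their interaction, and the random factor is subject ID". Estimation is by GEE: "we analyzed the data using generalized estimating equation (GEE) in SAS using PROC GENMOD". The effect is defined through change, so the group-by-time term carries the treatment comparison. The same section adds: "The obtained preliminary data will refine our power analysis to provide a more precise estimation of sample size for a future full trial".

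Section D sets out three visits (anodal, cathodal, sham) separated by a wash-out of at least two weeks. On allocation, the sentence beginning "The sequence of the stimulations will be" says only that the order is randomised and double-blinded. The supplied text does not name the orders used or mention blocking, a Latin square or counterbalancing.

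Two other statements in Section D bear on visits: "Baseline measurement will be performed at the beginning of the study on the first visit", and, as the carry-over check, "we will compare the outcomes of pre-stimulation measurement with the baseline for each visit". Aim 1 in Section A expects to "retain most of them to complete this trial", so some lost visits are foreseen.

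**The concern.** A visit effect can take two forms. If visit shifts the level of the score, as slow recovery would, pre and post move together and the shift cancels in group-by-time. If visit alters the within-visit change, as practice or novelty at visit 1 might, nothing in the model absorbs it.

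The second form is plausible. The primary outcome is a performance test repeated before and after stimulation at every visit. If the first-visit baseline is separate from the pre-stimulation measurement, visit 1 also carries an extra round of assessments. The direction and size of any effect are unknown.

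The safeguards in the plan do not reach it. The wash-out and the carry-over check concern pre-stimulation levels, so they can neither detect nor remove a difference in change between visits.

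Two things are at stake. With balanced orders, visit variation goes into the error term and inflates a variance that may be carried into the full-trial sample size. With unbalanced orders or lost visits, the realised active-minus-sham contrast is itself displaced.

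**Working it through.** **Plan's own figure.** The only calculated sample size is 40 for the full trial (Sections A and D). Its inputs are not given, so it cannot be reproduced. Back-solving a paired contrast gives (1.96 + 0.84)/√40 = 0.44 SD at two-sided 5% and 80% power. The point does not depend on this figure.

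**Inputs.** From the documents: 12 participants, three visits, three conditions, hence six possible orders. Assumed, because the documents give none:
- the within-person difference between two change scores has SD 1, so error variance is 0.5 per change score;
- δ, the extra change at visit 1, is 0, 0.25, 0.5 or 1 SD;
- the true effect is 0.89 SD.

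**Which term matters.** Take a noise-free GEE with no true effect, the change rising by 1 point per visit, and the 12 people split 3/1/3/2/2/1 over the six orders. Mean visit positions are anodal 1.917, cathodal 1.833 and sham 2.250. The planned model returns 1.917 − 2.250 = −0.33 for anodal and 1.833 − 2.250 = −0.42 for cathodal, versus sham. Adding visit alone leaves both unchanged; adding visit-by-time makes both 0. A pure level shift gives 0 in every model.

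**Balanced orders (two people per order).** The estimate is unaffected, but the residual is not. The visit 1 effect gives within-person deviations of 2δ/3, −δ/3 and −δ/3, whose squares sum to 2δ²/3. Over 12 people that is 8δ². Spread over 36 − 12 − 2 = 22 error degrees of freedom and divided by 0.5:

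estimated/true variance = 1 + (8/11)δ².

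Simulation results (40,000 trials; pre/post GEE, independence working correlation, anodal minus sham; KC = Kauermann-Carroll standard error with t on 11 df):

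| δ (SD) | 0 | 0.25 | 0.5 | 1 |
|---|---|---|---|---|
| Variance ratio without visit (formula) | 1.00 | 1.05 | 1.18 | 1.73 |
| Type I error, KC, without visit terms | 5.1% | 4.6% | 3.6% | 1.2% |
| Type I error, KC, with visit terms | 5.0% | 5.1% | 4.9% | 5.1% |
| Power, KC, without | 80% | 79% | 75% | 59% |
| Power, KC, with | 80% | 80% | 80% | 80% |
| Type I error, uncorrected robust z, without | 8.9% | 8.1% | 6.6% | 2.9% |
| Type I error, uncorrected robust z, with | 10.2% | 10.4% | 10.3% | 10.1% |

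**Unrestricted allocation.** The shift in anodal minus sham is δ × (anodal-first count − sham-first count)/12. A difference of 4 gives 4/12 = 0.33δ. The count difference has variance 12 × (1/3 + 1/3) = 8, so the shift has mean 0 and SD √8/12 = 0.236δ. A difference of 4 or more occurs in about 22% of allocations. Exactly two people per order arises by chance with probability 12!/(2⁶ × 6¹²) = 0.34%.

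**Lost visits.** Let two of 12 leave after visit 1, starting from balanced orders. The worst case is both anodal-first (or both sham-first). With all available visits the shift is (4/10 − 4/12)δ = 0.067δ. In completers only it is (4/10 − 2/10)δ = 0.20δ. With visit terms it is 0 for all 66 possible pairs.

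**The case against.** The strongest reply is that the harm is conditional and usually modest. Randomisation makes the shift average zero, and under unrestricted orders the average type I error without visit terms stays at 4.9–5.1% (least squares). At δ of 0.25 to 0.5 the balanced-order power loss is about 1 to 5 points. The fall to 59% needs a visit effect larger than the assumed treatment effect. The dropout shift is trivial if all available visits are used. This is a 12-person proof-of-concept study that claims no efficacy power.

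The visit terms can also hurt if adopted alone:
- With an uncorrected robust z, type I error rises to about 10%. Estimated variance is then about 0.82–0.84 of the true value, so a full trial sized from it would be too small. Without visit terms the uncorrected ratios are 0.91, 0.95, 1.08 and 1.59.
- With unrestricted orders, fitting visit raises the contrast variance by about 11% on average (35% at the 95th percentile), and power at δ = 0 falls from 84% to 80% (least squares). Squared error improves only above δ = √(0.108/12)/0.236 = 0.40 SD.
- When first-visit counts differ by 4, the KC test with visit terms runs at 5.7–6.0%, against 5.0, 5.3, 6.3 and 8.3% without them.

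On sample size, the SAP does not say that the variance will come from this model. With 22 degrees of freedom a 95% interval for a variance runs from 0.60 to 2.00 times the estimate, much wider than an inflation of 5–18%.

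All of this stands. It limits the weight of the point and shows that the terms, the standard error and the blocking belong together. It does not supply the missing term or the missing allocation rule.

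**Conclusion.** The concern holds. The model omits visit and visit-by-time, and the supplied text does not say that the orders are balanced. That second statement covers only the text available, which passes from Section J to Section L.

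There is no systematic bias. With balanced orders the estimate is sound, but the corrected test becomes conservative and the variance is overstated by a factor of 1 + (8/11)δ². With chance imbalance the realised contrast moves by 0.33δ when first-visit counts differ by 4. If the within-visit change is the same at all visits, nothing is lost.

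The sizes rest on assumed values of δ and on the 0.89 SD effect. The standard error is also an assumption, since the SAP names none. Confidence in the practical size is therefore moderate. The change is recommended because it is inexpensive and standard for a cross-over, not because the planned analysis is invalid.

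**What to change.** In Section L, add visit (1, 2, 3) and visit-by-time as fixed effects. Visit alone is not enough in the pre/post model; in a change-score model the equivalent is a period term. Pair this with a small-sample-corrected robust standard error and a t reference, for example Kauermann-Carroll, or use a linear mixed model on change scores with subject, condition and period. Analyse all available visits. Take the variance for the full-trial sample size from that model.

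In Section D, state that the six sequences are allocated in permuted blocks of six, which gives two participants per sequence at 12 and still works if more are enrolled.

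The cost is a few lines in the SAP and one sentence on allocation, with no new data. With balanced orders, error degrees of freedom on the change score fall from 22 to 20, or mean parameters in the pre/post GEE rise from 6 to 10. Power at δ = 0 is essentially unchanged: 80.0% without against 79.9% with (corrected GEE), and 83.8% against 83.4% (least squares).
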